**ADVERSE REACTIONS:** There are few side effects of UPA and LNG-IUS. These are listed in the protocol and informed consent form. Most side effects resolve spontaneously. Anticipated events means reactions to treatment previously observed that may require medical intervention but are not serious in nature.

All adverse events that occur will be recorded in the Source Documents. Adverse events should be captured in the medical history.

Adverse Events occurring will be captured and followed until the condition resolves, stabilizes, or is otherwise explained, or the subject is lost to follow-up. Subjects will be instructed that they may contact one of the Principal Investigator at any time throughout the course of the study.

The Investigator will review each event and assess its relationship to method of EC (not related, unlikely, possible, probable, and highly probable). The following definitions will be used for rating relationship to the treatments or investigational device:

- Not related – The event is clearly related to other factors such as the subject's clinical state, therapeutic interventions, or concomitant medications administered to the subject.
- Unlikely – The event was most likely produced by other factors such as the subject's clinical state, therapeutic interventions, or a concomitant medication administered to the subject; and does not follow a known response pattern to the investigational device.
- Possible – The event follows a reasonable temporal sequence from the time of investigational device administration; and/or follows a known response pattern to the study treatments; but could have been produced by other factors such as the subject's clinical state, therapeutic interventions, or concomitant medications administered to the subject.
- Probable – The event follows a reasonable temporal sequence from the time of investigational device administration; and follows a known response pattern to the investigational device; and cannot be reasonably explained by other factors such as the subject's clinical state, therapeutic interventions, or concomitant medications administered to the subject.

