- Highly Probable – The event follows a reasonable temporal sequence from the time of investigational device administration; and follows a known response pattern to the investigational device; and cannot be reasonably explained by other factors such as the subject's clinical state, therapeutic interventions, or concomitant medications administered to the subject; and either occurs immediately following investigational device administration, or improves on stopping the investigational device, or reappears on repeat exposure, or there is a positive reaction at the treatment site.

Each adverse event reported will be graded on a 3-point severity scale. The following definitions for rating severity will be used:

- Mild – easily tolerated, causing minimal discomfort, and not interfering with normal everyday activities.
- Moderate – sufficiently discomforting to interfere with normal everyday activities.
- Severe – incapacitating and/or preventing normal everyday activities.

**A Serious Adverse Event** is any adverse device experience that results in any of the following outcomes: death, a life-threatening adverse device experience, in-patient hospitalization or prolongation of hospitalization, a persistent or significant disability/incapacity, or a congenital anomaly/birth defect. Important medical events that may or may not result in death, be life-threatening, or require hospitalization may be considered a serious adverse device experience when, based upon appropriate medical judgment, they may jeopardize the subject or subject may require medical or surgical intervention to prevent one of the outcomes listed in this definition

If any of the above adverse events are serious as defined by the FDA Code of Federal Regulations (CFR), Title 21, special procedures will be followed. All serious adverse events will be reported within 24 hours of acknowledgment to the Medical Monitor whether or not the serious events are deemed treatment-related. All serious event reporting will adhere to 21 CFR part 812 and the IRB will be notified accordingly.

Adverse events, whether serious or non-serious, will be followed until the condition is resolved, stabilized, or otherwise explained, or the subject is lost to follow-up. Adverse events will be captured up to one week after a subject completes the study and where appropriate, medical tests and examinations will be performed to document the resolution of event(s).

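### The two highest causality grades and the SAE sentence are worded for the device only, so they do not fit events in the UPA arm

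*Combined protocol and SAP*

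**What the plan says.** The relevant text is in the ADVERSE REACTIONS section of the combined protocol and SAP.

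- The task covers both arms: "The Investigator will review each event and assess its relationship to method of EC". The lead-in to the five grades agrees: "The following definitions will be used for rating relationship to the treatments or investigational device".
- Unlikely needs two things: other factors most likely produced the event, and it "does not follow a known response pattern to the investigational device".
- Possible can be met by timing from the device, by a treatment pattern, or by both. Its second part reads "follows a known response pattern to the study treatments; but could have been produced by other factors".
- Probable requires timing from the device and also that the event "follows a known response pattern to the investigational device; and cannot be reasonably explained by other factors".
- Highly Probable repeats the conditions of Probable and adds one further feature: the event comes on immediately after the device is given, "or improves on stopping the investigational device, or reappears on repeat exposure, or there is a positive reaction at the treatment site".
- A Serious Adverse Event "is any adverse device experience that results in any of the following outcomes". The next paragraph, however, opens "If any of the above adverse events are serious as defined by the FDA Code of Federal Regulations (CFR), Title 21". It then requires 24-hour reporting to the Medical Monitor regardless of relatedness.

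Not related and the three-point severity scale carry no device wording. UPA is described as an oral tablet, and no separate grading scale or SAE definition is given for it.

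**The concern.** The scale is meant to serve a device arm and a tablet arm, but its top two grades can be reached only through the device. Investigators who apply the text as written would grade like events differently by arm, and sites that read it by intent would differ from sites that read it literally. The PROTOCOL DEVIATIONS section allows no departure without approval outside a medical emergency, so a literal reading cannot be ruled out.

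What is at stake is the descriptive safety comparison. The distortion runs against the LNG-IUS, the method under test. Safety is not one of the stated aims, and neither the sample size nor the pregnancy analysis uses these grades.

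**Working it through.** The plan states no figure on this point, so the check is to apply each definition, condition by condition, to an event in a woman who took UPA and has no device.

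| Grade | Conditions | Can a UPA event meet it literally? |
|---|---|---|
| Not related | Clearly due to other factors | Yes |
| Unlikely | Most likely other factors, and no known device pattern | Yes; a UPA pattern is never tested |
| Possible | Device timing and/or treatment pattern, and other factors could explain it | Yes, through the treatment pattern, but only if another cause is plausible |
| Probable | Device timing, and device pattern, and no other reasonable explanation | No; two mandatory conditions name the device |
| Highly Probable | As Probable, plus one further feature | No, for the same reason |

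Three results follow.

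1. The highest literal grade for UPA is Possible.
2. A UPA reaction with no other explanation fails Possible, because that grade needs a rival cause. It fails Probable, because that grade needs the device. It therefore fits no grade.
3. Unlikely is asymmetric only for events already judged most likely due to something else. Among those, one matching a known LNG-IUS pattern is kept out of Unlikely, while one matching only a known UPA pattern is not.

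**Effect by cut-off.** At Probable or higher, the literal UPA count is 0 of the planned 133, whatever the true number. At Possible or higher, UPA events graded Possible count. What is lost is any event that fits no grade, or that goes to Unlikely despite a UPA pattern. The documents do not say how many that would be.

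**Illustration at Probable or higher.** Abdominal pain is listed for both methods under Risks and Benefits: 12% for UPA (0.12 × 133 = 16.0 women) and 12.8% for the LNG-IUS, as abdominal/pelvic pain (0.128 × 399 = 51.1 women at most, since cervicitis found after randomization stops insertion). Two quantities are assumed because the documents give neither: *s*, the share of these events with no other explanation, taken as equal in both arms; and *L*, the share of those UPA events graded literally.

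Gap (LNG-IUS minus UPA, percentage points) = 12.8*s* − 12.0*s*(1 − *L*) = 0.8*s* + 12.0*sL*

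| *s* | Neutral wording (*L* = 0) | *L* = 0.5 | *L* = 1 |
|---|---|---|---|
| 10% | 0.1 | 0.7 | 1.3 |
| 25% | 0.2 | 1.7 | 3.2 |
| 50% | 0.4 | 3.4 | 6.4 |
| 75% | 0.6 | 5.1 | 9.6 |

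The direction does not depend on *s* (if above zero) or on *L* (if above zero). The size depends on both.

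**SAE text.** A serious UPA event is not a device experience, so it falls outside the definition sentence. The Title 21 sentence that follows is not limited to the device, and the 24-hour rule ignores causality. The two paragraphs disagree on what counts as an SAE in the UPA arm, but a route to report such an event exists.

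**The case against.** The strongest reply is that this is loose drafting which nobody would follow to the letter. The governing sentence and the lead-in both cover the two arms, Possible mixes device and treatment wording in one sentence, and the coordinating center trains all sites. Moreover, the statistical sections specify no summary by causality grade, so the bias falls on an output the plan does not name. These points stand as limits on consequence. They do not repair the definitions, and clear intent to cover both arms is a reason to make the text say so.

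Several stronger readings are tempting, and the documents do not support them.

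- *A reader might infer that serious UPA events would go unreported.* All adverse events are recorded, the Title 21 sentence and the 24-hour rule apply, and the Study Communications Plan sends any adverse event to the principal investigator immediately.
- *A reader might infer that every by-arm report of related events would be badly distorted.* The protocol sets no cut-off for related. UPA falls to zero by construction only at Probable or higher.
- *A reader might infer that typical UPA reactions, such as headache, would be graded Unlikely.* That grade first requires that other factors most likely caused the event, so a headache attributed to UPA does not qualify.
- *A reader might take a gap of 3 to 10 points as the expected bias.* That range needs assumed shares of 25% to 75% and fully literal grading at every site. It also applies the listed rates to all randomized women, with no allowance for the roughly 20% loss to follow-up planned by 6 months.
- *A reader might infer that the study report is barred from tabulating adverse events.* The reporting section says what the report will include; it does not restrict it to that.

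**Conclusion.** The point holds as a minor correction to the safety definitions. As written, the rule produces a wrong grade, or none, for a UPA event with no other explanation, and the SAE definition is internally inconsistent for that arm. That conclusion rests on the wording alone.

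The predicted bias is conditional. It needs at least some literal grading and a by-arm summary that uses the grades. The tabulated gaps of 0.7 to 9.6 points under literal or half-literal grading show how the mechanism scales for one symptom and are not an estimate. No effect on SAE counts can be derived from the documents.

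**What to change.** In the ADVERSE REACTIONS section:

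1. In Unlikely, Possible, Probable and Highly Probable, replace the references to the investigational device and to the study treatments with *EC method received (UPA or LNG-IUS)*.
2. Define an SAE as any adverse event in either arm with one of the listed outcomes, and remove the device wording from the rest of that paragraph.
3. Combine Probable and Highly Probable in any by-arm summary. Even after rewording, improvement on stopping and a reaction at the treatment site cannot apply to a single oral dose, so UPA has fewer ways to reach the top grade.

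The cost is a wording amendment with IRB review, a reminder to sites, and a short re-grade of events already rated. No new data are needed: staff watch the participant take UPA at enrollment, so timing from administration is known in both arms. The change may bring a few more SAE reports from the UPA arm.

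A descriptive adverse event table by treatment received would be a sensible but separate and optional addition to the Data Analysis/Statistical Methods section.

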### **Research Design and Methodology:**

Research design and general methodological approach: We will perform a randomized control trial comparing oral UPA to LNG-IUS for emergency contraception. We will prospectively enroll 532 women experiencing an act of under-protected intercourse within the previous 5 days (120 hours). Participants with a negative pregnancy test, and who meet all inclusion criteria, will be randomized to either an immediate LNG-IUS insertion or oral UPA EC regimen (30mg ulipristal acetate) in a 3:1 ratio. Participants will be provided with a pregnancy test to perform at home and will be called to report the results of the urine pregnancy test 5-6 weeks after insertion. Participants receiving the LNG-IUS will also be return for a brief visit to check LNG-IUS strings. Participants will be contacted via telephone at 6 and 12months post enrollment to complete a follow-up survey. The primary outcome of this study is observed pregnancy rates at 5 weeks and 6 months after enrollment.

Criteria for selection of subjects: Potential participants for this study will be identified in as follows: 1) Women enrolled in the Contraceptive CHOICE Project (CHOICE) who are not currently using a long acting reversible contraceptive (LARC) method and have experienced an act of under-protected intercourse in the previous 5

days; 2) Women presenting, either in person or via telephone contact, to the Barnes Jewish Hospital Women's Health resident OB/GYN clinic who have experienced an act of under-protected intercourse in the previous 5 days; 3) Women identified from an advertising campaign; and

Enrollment: All potential participants receive informed consent and will be directed to make an appointment for consent, randomization, and allocation of method.

Inclusion Criteria:

- Women age 14-45
- Under-protected intercourse within the last five days (120 hours)
- Willingness to accept either IUS intervention or oral EC
- Ability and willingness to follow-up via telephone for results of a urine pregnancy test (UPT)
- Ability and willingness to be contacted by phone for 6 and 12 month follow-up

Exclusion Criteria:

- Positive pregnancy test
- Non-English speaking
- Contraindication to intrauterine contraception or oral UPA
  - Active cervicitis, PID, or recent post-abortal or postpartum infection
  - Undiagnosed abnormal uterine bleeding
  - Known or suspected cervical or endometrial neoplasia

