Outcomes may be classified as resolved, improved, unchanged, worse, fatal, or unknown (lost to follow-up). Following the resolution of any study-associated adverse events there will be no further adverse event reports for that subject.

**PROTOCOL DEVIATIONS:** No deviations from this protocol will be permitted, except in a medical emergency, without the approval of the Coordinating Center/Sponsor. Any amendment to this study will be discussed by the Investigators and the Coordinating Center. If agreement is reached concerning the need for modification, this will be made in a formal amendment to the protocol. All requests for protocol deviations must be approved by the IRB. If a deviation occurs, the Investigator must inform the Sponsor and IRB in writing within 10 days.

**DATA COLLECTION AND MONITORING:** The coordinating center (WashU/sponsor) will train all investigative sites. The sponsor will also monitor the site at various intervals and upon request expects to receive intermediate results by fax following each visit to evaluate treatment progress in accordance with the sponsor's monitoring procedures and guidelines. Case Report Forms and Investigator Binders will be reviewed for current data. The sponsor will collect data at the end of the follow-up period. The sponsor will list the study on clinicaltrials.gov as required by FDA regulations.

**CONFIDENTIALITY AND DISCLOSURE OF MEDICAL INFORMATION:** As part of this study the Investigator and the team at each research facility will keep records of subject participation in the study. These study records will include personal information that the subjects provide including age, sex, etc., the results of the study, information about response to treatments, and other medical information relating to participation in the study. Under federal law the study records cannot be used or disclosed by the research Investigator for research purposes unless subjects sign the informed consent authorization.

The sponsor and its consultants will analyze and evaluate study results and information and may report them to the U.S. Food and Drug Administration (the FDA) or other regulatory agencies in the United States. Study records will be assigned a code number by the study team and the subject will ordinarily not be identified by name in the study records that are sent to the Sponsor and its consultants. However, The Sponsor and its consultants will have the right to see the complete study records.

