### Pregnancy

UPA is 93-94% effective in preventing pregnancy

LNG-IUS: We hypothesize the LNG-IUS will be as effective as the Copper IUD for EC

If participant reports a positive pregnancy test, we will: 1) invite the participant in for pregnancy testing and transvaginal ultrasound to confirm location and dating of pregnancy. If the LNG-IUS is in place and intrauterine pregnancy is confirmed, we will recommend and complete removal of IUD.

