### Pregnancy with IUD

Increased risk of spontaneous abortion

Increased risk of infection in the uterus

Early delivery of fetus if pregnancy continued and IUD left in place

The impact of increased EC access (some forms are now available over-the-counter) on population outcomes and concluded that although use of has EC increased, there has been no demonstrable reduction in unintended pregnancy. By contrast, increased uptake of IUDs in an at-risk population has been shown to dramatically reduce unintended pregnancy and abortion rates. The continued highly effective pregnancy prevention the IUD provides beyond the post-coital period offers a unique opportunity to effect change in the stagnant unintended pregnancy and abortion rates in this country.

Use of the LNG-IUD as an EC method has tremendous public health implications. The device is extremely well liked by users indicating women will continue using it beyond the immediate risk behavior. The numerous non-contraceptive benefits of the LNG-IUD and improved bleeding profile have led to increase uptake when compared to the copper IUD.

Increasing the number of women using IUDs in the post-coital period has the potential to decrease long-term unintended pregnancy and abortion rates in a way that oral regimens have not been able to. Despite improved access to emergency contraception with over the counter availability, rates of unintended pregnancy in the US have not.

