#### 12-month follow-up

##### Phone call (less than 10 minutes)

- Participant is called and asked if she has time to complete 12-month follow-up or would like to schedule an additional call for a more convenient time
- If scheduling a call,
  - Schedule a call for an appropriate time
- Completing 12-month follow-up,
  - Verify participant's date of birth (DOB)
  - Verify contact information
  - Administer 12-month follow-up in RedCap
  - Ask participant if she has any questions
  - Fill out tax office paperwork
  - Mail gift card
  - Thank participant for participating in the LIFE study

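### Continuing pregnancies are not followed to outcome, and adverse event capture closes near week 53, before term births from conceptions after about week 15

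*Combined protocol and SAP*

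**What the plan says.** The combined protocol and SAP deals with this in four places.

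- **Harms named.** The serious adverse event definition under ADVERSE REACTIONS includes "a persistent or significant disability/incapacity, or a congenital anomaly/birth defect". The Pregnancy with IUD section lists spontaneous abortion, uterine infection and "Early delivery of fetus if pregnancy continued and IUD left in place".
- **Closing rule.** "Adverse events will be captured up to one week after a subject completes the study". Completion is not defined. The design section says "Participants will be contacted via telephone at 6 and 12months post enrollment to complete a follow-up survey", and the 12-month call ends with the step "Thank participant for participating in the LIFE study", so completion is most naturally that call.
- **Events already on record.** "Adverse events, whether serious or non-serious, will be followed until the condition is resolved, stabilized, or otherwise explained, or the subject is lost to follow-up". A further rule says "Following the resolution of any study-associated adverse events there will be no further adverse event reports for that subject".
- **What happens on a positive test.** The Measures paragraph provides for validation and options counseling. The Pregnancy section adds an ultrasound for location and dating, and then: "If the LNG-IUS is in place and intrauterine pregnancy is confirmed, we will recommend and complete removal of IUD". The telephone surveys cover new diagnoses, pregnancies since enrollment and STIs. Delivery, pregnancy outcome and the infant are not among the listed items.

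**The concern.** The plan names a harm that is often recognised only at birth, and then sets a closing date that some of the births will pass. No later contact is tied to a pregnancy. The LNG-IUS is studied here under an IND, for a use the protocol describes as not yet evaluated, and the sample size calculation itself expects pregnancies in both arms. Few are expected with the device, so each unknown outcome weighs heavily. If the final report lists no anomalies, a reader could not tell whether none occurred or whether some of the births came after the window closed.

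**Working it through.** The documents give no figure for this point, so there is nothing to reproduce. The check is calendar arithmetic.

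**Inputs**
- Last contact: 12 months, taken as week 52 (Research Design and Methodology; 12-month follow-up).
- Capture after completion: 1 week (ADVERSE REACTIONS).
- Assumed 6-month pregnancy rates: 11% UPA and 2% LNG-IUS. Enrolled: 133 and 399. Loss by 6 months: about 20% (Power Analysis and Sample Size).
- Gestational lengths are my assumption: term 40 weeks (range 37 to 42), preterm 20 to under 37, spontaneous abortion under 20. Weeks from conception = gestational weeks − 2.

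**Step 1: window.** 52 + 1 = week 53 after enrollment.

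**Step 2: latest conception whose event falls inside it** = 53 − weeks from conception to event.

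| Event | Gestational weeks | Weeks from conception | Latest conception week |
|---|---|---|---|
| Birth, late | 42 | 40 | 13 |
| Birth, term | 40 | 38 | 15 |
| Birth, early term; upper limit for preterm | 37 | 35 | 18 |
| Preterm delivery | 34 | 32 | 21 |
| Preterm delivery | 28 | 26 | 27 |
| Earliest preterm; upper limit for spontaneous abortion | 20 | 18 | 35 |
| Spontaneous abortion | 13 | 11 | 42 |
| Spontaneous abortion | 8 | 6 | 47 |

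An immediate failure, conceived near week 0, reaches term near week 38, which is 53 − 38 = 15 weeks before closure.

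**Step 3: upper bound on the number affected, conceptions through 6 months.**
- Pregnancies among women followed: LNG-IUS 0.02 × 399 × 0.8 = 6.4; UPA 0.11 × 133 × 0.8 = 11.7; total 18.1.
- With conceptions spread evenly over 26 weeks and all going to term, the share undelivered at closure is (26 − 15)/26 = 42%.
- LNG-IUS: 6.4 × 11/26 = 2.7. Both arms: 18.1 × 11/26 = 7.7.
- With a cut-off at week 18, the share is 8/26 = 31%, giving 2.0 and 5.6. With week 13, it is 13/26 = 50%, giving 3.2 and 9.0.

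**Step 4: months 6 to 12.** Every conception in this period (week 26 or later) that goes to term delivers at week 64 or later, outside the window. The documents give no rate for these months, so no count is offered.

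**The case against.** The case on the other side has five parts.

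1. *The investigational question is emergency contraception.* Immediate failures deliver well inside the window. Conceptions after week 15 are failures of ongoing contraception, for which the device is already approved, or in the UPA arm come long after a single dose. This stands, and it narrows the point considerably. It does not remove it: the primary outcome runs to 6 months, and Risks and Benefits weighs 6- and 12-month failures in deciding whether the trial continues.
2. *A pregnancy may itself count as an adverse event.* Risks and Benefits introduces its DSMB trigger for LNG-IUS pregnancies as part of adverse event monitoring. If so, the follow-until-resolved rule could carry a detected pregnancy to its end. The text is at most ambiguous: pregnancy is the primary outcome, and no section says that it is an adverse event. An anomaly first seen at a birth after week 53 would be a new event, not one already being followed.
3. *Existing contacts may pick outcomes up.* The 6- and 12-month surveys ask about diagnoses and pregnancies, and women may contact an investigator at any time during the study. That helps for events inside the window, but it relies on women volunteering an outcome that the listed items do not ask for.
4. *Few of the counted pregnancies bear on the device.* About 5.0 of the 7.7 (11.7 × 11/26) are in the UPA arm. Many unintended pregnancies will not continue, and device removal is planned. This stands; the counts are ceilings.
5. *Later contact and infant data may need new consent.* This also stands and belongs in the cost.

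A reader might go further and infer that all the named harms are lost for conceptions after week 15. The arithmetic does not support that. Week 15 applies to term birth only. Spontaneous abortions fall inside the window for conceptions to about week 35, and all preterm deliveries to about week 18, with earlier preterm deliveries inside it for later conceptions still. Anomalies may also be found before birth. A reader might likewise apply the rates to all 532 women; that overstates the counts, because 532 already allows for the 20% loss.

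**Conclusion.** The gap is real but narrow. As written, the plan does not follow continuing pregnancies to outcome, and the window excludes term-birth outcomes, including an anomaly first found at birth, for conceptions after about week 15 (13 to 18 for births at 42 to 37 weeks). For spontaneous abortion, most early deliveries and immediate failures, the only shortfall is the missing outcome question.

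The ceiling for conceptions in the first 6 months is about 2.7 LNG-IUS pregnancies and 7.7 in all. It rests on the plan's assumed rates, 20% loss, even spread of conceptions, all pregnancies going to term, and completion meaning the 12-month call. Terminations, losses and clustering of conceptions near enrollment lower it; conceptions in months 6 to 12 that go to term add to it. No efficacy aim or analysis is affected. It is worth correcting because it concerns a serious adverse event that the protocol itself defines, and the correction is cheap.

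**What to change.** - **ADVERSE REACTIONS:** after the one-week rule, add that for any woman known to be pregnant before study completion, capture stays open until the pregnancy outcome is known or she is lost to follow-up. Say how this fits with the follow-until-resolved rule and the rule ending reports after resolution.
- **Pregnancy section:** add one call, in both arms, after the due date derived from the planned ultrasound. Record the outcome (spontaneous abortion, termination, extrauterine pregnancy, preterm or term birth), any infection or congenital anomaly, and whether the device was in place.
- **Study report:** list these outcomes by arm.

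This is data collection only and changes no clinical rule. It takes a protocol amendment, a likely consent amendment, and roughly 10 to 20 calls by existing staff; the ceiling through 6 months is 18, plus any conceptions in months 6 to 12. The downside is that last contact for a few women falls up to about 9 months after the 12-month call (conception just before week 52 plus 38 weeks), with a short safety addendum to the report. The primary analysis and its timing are unchanged.
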